This study will investigate the 'diagnostic accuracy' of diarrhoea self-report for enteric infection by evaluating against the sampling of stool for analysis of faecal pathogens and biomarkers of infection. Not only does this provide a means to estimate the association between infection and reported diarrhoea, but it also allows for measurement of asymptomatic infection – which is still a target of WASH interventions. This study will randomise participants into one of two diarrhoea measurement arms for surveys: a basic survey for infant diarrhoea (similar to DHS) and an enhanced survey for infant diarrhoea (using tools such as the Bristol stool scale); and subsequently randomly selecting a subgroup from each arm to undergo faecal stool testing of infants. The primary outcomes will be the positive and negative predictive values of self-reported diarrhoea for enteric infection. As a secondary outcome we will examine the types of pathogen present. We would conduct a survey at baseline in February/March, a time with low diarrhoeal disease incidence; and June/July, a time with high diarrhoeal disease incidence - to account for seasonality, and to measure variation in respondent fatigue for the various methods. This research will take place in the Cox's Bazar refugee camp, which may also allow for analysis of the burden of carriage of disease which is not endemic to Bangladesh.

Background

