The study will follow a two arm RCT design in which 400 households will be recruited through random household sampling in both the formal and informal refugee camps in Cox's Bazar (Fig.1). The random household sampling will use an EPI sampling method, in which a series of random angles and distances from a pre-determined central point (e.g. a water tap) will be generated, selecting households closest to the mapped location. This list will be generated at the beginning of the data collection period, with households randomly assigned to each research assistant.

Inclusion and exclusion criteria

Inclusion and exclusion criteria for the study is as follows:

Inclusion	Exclusion
Household has at least one child under the age of five	Household is expecting to relocate/resettle/repatriate in the next 6 months
Household has at least one adult over the age of 18	
Household consents to study	

Recruitment

Households will be initially contacted by research assistants travelling door to door who will ask to speak with an adult in the household. The study will be explained through the use of the participant information sheet, with households meeting inclusion criteria being consented and enrolled in the study. As part of consenting, GPS coordinates, name, and mobile phone number will be recorded. Households who do not consent will not have mobile phone numbers recorded, but will have GPS coordinates recorded to ensure that the house is not approached again. Mobile phone numbers and GPS coordinates will be recorded separately from data in a log book, and linked to individual household identifiers which will be recorded on the survey form.

Diarrhoea survey

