Households will be randomised in a 1:1 ratio into the basic survey, a survey asking if a child had diarrhoea and dysentery in the past two weeks, based on DHS survey measures; and the enhanced survey, based on qualified stool charts (of which images will be displayed on the tablet during surveying), proxies for diarrhoea (such as oral intake), and measures of waterwashed diseases. All households will also be administered a basic demographic survey with questions on education, health, living environment, and WASH usage. If a household reports dysentery, they will be given the information of a local clinic for treatment. All surveys will be translated into Rohingya, and back translated into English – with translation following WHO guidelines: aiming for the simplest translation with the conceptual equivalent, targeted toward the target audience or Rohingya refugees, many of whom are illiterate with a low level of education. This will be done through consultation with Rohingya community members to ensure proper translation.

Data collection will take place at two time points: February/March and June/July. Research assistants will collect data through the use of ODK on an Android tablet. Data will be stored on the tablets and uploaded to Warwick servers at the end of each day, when research assistants return to the base office. Data will be additionally verified daily.

Stool sampling

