Within each arm at each time point, 20 households reporting diarrhoea, and 20 not reporting diarrhoea, will be selected to have the oldest infant under 5 undergo stool testing - a total of 80 households at each time point, 160 in total. The first 20 households reporting diarrhoea and not reporting diarrhoea in each arm will be selected and asked if they are willing to provide stool samples. A WhatsApp group will be created for the research assistants to determine when 20 consenting households have been reached in each arm. The consenting households will be given a stool collection container once the survey has been administered, which will be collected the following day. All stool containers will be labelled with a barcode which will be scanned by the research assistant using a tablet, to link the stools sample with the survey. Stool will be collected by the carer, and tested for the presence of predetermined organisms which are endemic to the Rohingya population, along with a small number of select pathogens that are not endemic (Table 1); and for the presence of biological markers of infection: calprotectin and lactoferrin. This will be done through the use of polymerase chain reaction analysis (PCR) at the laboratory at the ICDDR,B in Dhaka, Bangladesh. Stool will also be tested for blood using a faecal hemooccult test.

Туре	Species	Carriage period (adults)	Carriage period (children)
Bacteria	Shiga toxin-producing Escherichia	17-18 days (1)	35-69 days (2)
	Enteropathogenic Escherichia coli	ND	20—36 days (2)
	Enterotoxigenic Escherichia Coli	ND	<5 days (2)
	Enteroinvasive Escherichia Coli	ND	ND
	Enterohemorrhagic Escherichia Coli	ND	2-62 days (2)
	Salmonella typhi	12-25 days (3)	Varies (2)
	Salmonella paratyphi	28-55 days (4)	~30 days (2)
	Campylobacter	14-21 days (5)	Up to 6 weeks (5)
	Shigella	~28 days (6)	1-10 days (6)
	Cholera	~2 days (7)	~4 days (7)
	C. difficile	6-57 days (8)	6-57 days (8)
	C. perfringens	ND	ND
	Acinetobacter	7-11 days (9)	ND
Protozoa	Entamoeba histolytica	ND	ND
	Cryptosporidium	~8 days (10)	~8 days (10)
	Cyclospora	5-13 days (11)	22-23 days (11)
	Giardia	2-6 weeks (12)	~6 months (13)
Helminth	Ancylostoma duodenale	1-2 years (14)	ND
	Ascaris lumbricoides	Years (15)	Years (15)
Viruses	Rota-virus	Up to 35 days (16)	4-57 days (2)
	Hepatitis A	~21 days (17)	Up to 21 days (12)
	Hepatitis E	3-4 weeks (18)	ND
	Norovirus	ND	8-60 days (19)
	Human Caliciviruses	~14 days (20)	~12 days (20)
	Adenovirus	ND	8-23 days (20)

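### Stool samples go to the first 20 reporters and first 20 non-reporters in each arm, not to the random subgroup the summary promises, so PPV and NPV come from different parts of each round

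*Protocol*

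**What the plan says.** The Executive Summary names the positive and negative predictive values of self-reported diarrhoea as the primary outcomes. It describes the design as randomising households to a survey arm and "subsequently randomly selecting a subgroup from each arm to undergo faecal stool testing of infants".

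The Stool sampling section fixes the number: "Within each arm at each time point, 20 households reporting diarrhoea, and 20 not reporting diarrhoea", which makes 80 households per round and 160 in all. It then fixes the selection rule: "The first 20 households reporting diarrhoea and not reporting diarrhoea in each arm will be selected". The field control is a running count: "A WhatsApp group will be created for the research assistants to determine when 20 consenting households have been reached in each arm". Containers are handed out after the survey and collected the next day.

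On the households themselves, the Sampling section says "400 households will be recruited through random household sampling". Locations come from random angles and distances around a central point. The list is made at the start of data collection, and households are allocated to research assistants at random. No order of visits is stated. The Diarrhoea survey section adds "Households will be randomised in a 1:1 ratio into the basic survey" and "Data collection will take place at two time points: February/March and June/July".

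**The concern.** The two descriptions of who gives stool are incompatible, and the one that field staff would follow is the consecutive quota. That rule fills the two kinds of cell at very different speeds, because non-reporters are common and reporters are not. The non-reporter cell closes early in the round, while the reporter cell stays open much longer.

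NPV is then estimated from the opening part of each round and PPV from a longer stretch. Three things can enter NPV, and the contrast between reporters and non-reporters:

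- a calendar trend in infection within the round;
- an area trend, if households are not visited in random order;
- a difference between research assistants who work fast and those who work slowly, because the fast ones fill more of the early quota.

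Analysis cannot undo this. Once the cell closes, no later non-reporter stool exists to model or reweight.

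**Working it through.** **Inputs from the protocol.** 400 households allocated 1:1, so 200 per arm (Sampling; Diarrhoea survey). Quota of 20 per cell (Stool sampling). Prevalence of reported diarrhoea 10%; stated precision ±4 points for prevalence and ±7 points for predictive values of 90% (Data analysis). 28 travel days for each of four research assistants (Appendix 2).

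**Inputs assumed here.** Prevalence 5-30% and consent to give stool 50-100%. The protocol gives neither a June/July prevalence nor a consent rate.

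**The plan's own figures.** The half-width is 1.96 × √(p(1−p)/n).

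- Prevalence: 1.96 × √(0.1 × 0.9/200) = 4.2 points, which matches ±4. With 100 per arm it would be 5.9, so the plan evidently surveys all 200 per arm in a round.
- Predictive values: 20 × 2 arms × 2 rounds = 80, and 1.96 × √(0.9 × 0.1/80) = 6.6 points, which matches ±7.

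**When each cell closes.** With prevalence p and consent c, the expected number of interviews per arm is 20/((1−p)c) for non-reporters and 20/(pc) for reporters.

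| p | c | Interviews to 20 non-reporters | Share of 200 | Interviews to 20 reporters |
|---|---|---|---|---|
| 5% | 100% | 21.1 | 10.5% | 400 (not reached) |
| 10% | 100% | 22.2 | 11.1% | 200 |
| 10% | 80% | 27.8 | 13.9% | 250 (not reached) |
| 10% | 50% | 44.4 | 22.2% | 400 (not reached) |
| 20% | 100% | 25.0 | 12.5% | 100 |
| 30% | 100% | 28.6 | 14.3% | 67 |
| 30% | 50% | 57.1 | 28.6% | 133 |

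Here, not reached means that the expected number of interviews exceeds the arm. At 10% and full consent, the 95% range (negative binomial) for closing the non-reporter cell is 20 to 26 interviews. The chance of finding at least 20 reporters among 200 is 0.53.

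**In days.** Both non-reporter cells close after about 2 × 22.2 = 44.4 interviews. If the 28 travel days are split evenly over two rounds (assumption), 400/14 = 28.6 interviews a day and 44.4/28.6 = 1.6 days. If each round has 28 days, 400/28 = 14.3 a day and 44.4/14.3 = 3.1 days.

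**Effect on NPV.** Let E be infection prevalence among the early non-reporters and W that among all non-reporters in the round. The bias is (1−E) − (1−W) = W − E, one for one. With equal numbers of stools per round, a gap in one round only is halved in the pooled value:

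| Gap W − E (assumed) | Bias, that round's NPV | Bias, pooled NPV, gap in one round |
|---|---|---|
| 5 points | 5 | 2.5 |
| 10 points | 10 | 5 |
| 20 points | 20 | 10 |

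The gap is taken to be the same in both arms.

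**What a random draw would do.** At 10% prevalence and full consent it takes 20 of 180 non-reporters (1 in 9), spread over the whole arm. The expected number of stools, and so the ±6.6 points, does not change.

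**The case against.** **Randomness upstream.** Locations are random and households are allocated to the four research assistants at random. If visits follow list order, the first 20 non-reporters are close to a random draw from the area. This stands as a limit on the geographic argument. A reader might infer that the non-reporter stools come from a few neighbouring spots. The documents do not support that as fact, because the order of visits is not stated. The calendar mismatch remains even with a random order.

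**Higher incidence in June/July.** The picture of reporters spread over the whole round holds only near 10% prevalence. At 20-30% the reporter cell would close after about 100 to 67 interviews. This also stands. The windows still differ: 25 against 100 interviews at 20%, and 29 against 67 at 30%.

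**No gradient is shown.** Many child carriage periods in the organism table run to weeks or longer (enteropathogenic *E. coli* 20-36 days, norovirus 8-60, *Giardia* about 6 months). Infection with those organisms should move slowly within a round. Enterotoxigenic *E. coli* and cholera have short periods and are exceptions. A reader might infer a large bias, say 20 points, and set it against the stated ±7. Nothing in the documents supplies such a gap, and the ±7 applies to values of 90% with 80 stools. At values of 50-70% the half-width with 80 stools is about ±10 to ±11 points.

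**Interval method.** It would also go too far to fault the plan for a simple binomial interval in the analysis. The Data analysis section names no method. Only its precision statement agrees with one.

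**Consents or stools.** Counting consents is a matter of yield, separate from selection. It is also unclear whether only the first 20 are asked or asking continues until 20 agree.

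**Conclusion.** The contradiction between the Executive Summary and the Stool sampling section is plain, and it concerns the sample behind both primary outcomes. Followed as written, the Stool sampling rule closes the non-reporter cell after about 11% of interviews in the arm at the plan's 10% prevalence, and after 10.5-28.6% over the assumed ranges. Reporter stools come from a longer window, up to the whole round at 10%.

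This rests on 200 households per arm being surveyed in each round, which the ±4 points supports, and on the assumed consent and June/July prevalence. The size and direction of any bias in NPV cannot be derived from the documents. The table of gaps shows how it would carry through and does not estimate it.

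The point should be fixed before fieldwork. It does not rank higher because the sampling upstream is already random and no gradient is documented.

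**What to change.** Replace the first-come rule in the Stool sampling section with a random draw made by the tablet in ODK. Show the result only after the diarrhoea questions are complete, and run the draw through the whole round in each arm.

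- **Non-reporters:** before each round, set an invitation fraction that yields about 20 stools per arm. At 10% prevalence this is 20/180, about 1 in 9, with full consent, and 20/(180 × 0.8) = 0.139, about 1 in 7, with an assumed 80% consent.
- **Reporters:** invite all of them only where about 20 or fewer per arm are expected. Otherwise use a preset random fraction, so that the planned 80 stools per round is kept. Inviting every reporter in June/July at an assumed 20-30% prevalence and 80% consent would give 400 × 0.2 × 0.8 = 64 to 400 × 0.3 × 0.8 = 96 reporter stools, against 40 planned. Appendix 2 prices tests at 129 USD each and budgets 120, already fewer than the 160 stools planned.
- **Counting:** count each cell on barcoded stools received, not on consents.

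The cost is a few lines of form logic and a revised sentence in the protocol. The downside is that cell sizes vary around 20 (about 12 to 29, 95% binomial range, with simple random invitation; less with systematic selection), and containers must be issued throughout the round.

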	Astrovirus	ND	1-10 days (20)
Fungi	Enterocytozoon	18-38 days (21)	9-40 days (22)

Informed consent

All respondents will be consented in the Rohingya language and given a demographic and behaviour survey at the first time point. All questionnaires and surveys will be translated into Rohingya and back translated into English, with all data collection will be completed by Rohingya research assistants.

Data analysis

Data will be analysed using Stata version 15. The following analyses will be conducted

- Incidence rate ratios and associated 95% confidence intervals comparing diarrhoea and dysentery incidence between:
 - o Enhanced and basic surveys
 - o Survey method and stool analysis method
- Positive predictive value and associated 95% confidence interval of reported diarrhoea for the presence of enteric pathogens
- The association between diarrhoea presence and other potential markers of enteric infection such as MUAC and water-related diseases, measured for example by Jaccard's index
- A logistic regression of diarrhoea prevalence on demographic and health variables to examine association.

All missing data will be reported and assumed to be missing at random. The sample sizes proposed here would give us power to estimate the self-reported diarrhoea rate in each arm to a 95% confidence interval of approximately ±4 percentage points, assuming a point prevalence of 10%. We would also be able to estimate the positive and negative predictive values to approximately ±7 percentage points assuming values of 90%.

Data Management

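### Stool recruitment closes on consents, but the design and its ±7 points need 20 tested stools in each arm-by-report cell, and no allowance for non-returned stools is stated

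*Protocol*

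**What the plan says.** In the protocol, under Design and Methodology, Stool sampling, the design is set per arm and per report status: "Within each arm at each time point, 20 households reporting diarrhoea, and 20 not reporting diarrhoea, will be selected" for stool testing. The totals are explicit: "a total of 80 households at each time point, 160 in total".

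The same paragraph then says how the households are found: "The first 20 households reporting diarrhoea and not reporting diarrhoea in each arm will be selected and asked if they are willing" to give a sample. The field counter follows: "A WhatsApp group will be created for the research assistants to determine when 20 consenting households have been reached in each arm". Receipt of the stool comes later: "The consenting households will be given a stool collection container once the survey has been administered, which will be collected the following day".

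The Data analysis section rests its precision on this subsample: "We would also be able to estimate the positive and negative predictive values to approximately ±7 percentage points assuming values of 90" per cent. On losses it says only that missing data will be reported and treated as missing at random. Nothing in the protocol inflates the quota for non-return, reopens a place when no stool comes back, or says that the count is of stools received.

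**The concern.** The Executive Summary names the positive and negative predictive values as the primary outcomes, and only stools that reach the laboratory contribute to them. The field counter differs from what the design needs in two ways.

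- It counts households that agree, not stools that arrive. A household can agree, fill a place, and have nothing to hand over the next day. Followed as written, each such case takes its cell below 20 tested.
- It counts per arm, without report status. The design has two cells of 20 in each arm, so the counter does not say what is being filled.

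This is a recruitment rule, not an analysis choice. Once a round is over, no statistical analysis plan can recover stools that were not collected.

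**Working it through.** **Inputs from the protocol.** 400 households (Sampling) randomised 1:1 (Diarrhoea survey), so 200 per arm. 20 per report group, per arm, per time point (Stool sampling). Predictive values of 90% and prevalence of 10% (Data analysis).

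**Input assumed.** The share of consenting households that return an adequate stool. The protocol gives none; 90%, 80% and 70% are used here as a range.

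**1. The plan's own figures.** Cells: (20 + 20) × 2 arms = 80 per time point; × 2 time points = 160. Each predictive value uses one report group, so pooled over arms and rounds n = 20 × 2 × 2 = 80. Half-width = 1.96 × √(0.9 × 0.1 / n). With n = 80 this is ±6.57 points, which matches the stated ±7. Exactly ±7 needs n = 1.96² × 0.09 / 0.07² = 70.6, so 71.

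**2. Consent-based closing, no replacement.**

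| Assumed return | Stools per cell | n per predictive value | Half-width (points) | Consents needed for 20 stools per cell |
|---|---|---|---|---|
| 100% | 20 | 80 | ±6.57 | 20 |
| 90% | 18 | 72 | ±6.93 | 23 |
| 80% | 16 | 64 | ±7.35 | 25 |
| 70% | 14 | 56 | ±7.86 | 29 |

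The last column is 20 divided by the return rate, rounded up. The ±7 survives the loss of 80 − 71 = 9 stools per predictive value, about 11%. At 80% return the widening is 7.35 − 6.57 = 0.78 points; at 70% it is 1.29.

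**3. Are there spare households to refill a place?** At 10% prevalence each arm has about 200 × 0.9 = 180 non-reporters and 200 × 0.1 = 20 reporters per round. For non-reporters, 23 to 29 consents is easily met. For reporters, with the number distributed as Binomial(200, 0.10):

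- P(at least 20) = 0.53
- P(at least 23) = 0.27
- P(at least 25) = 0.15
- P(at least 29) = 0.03

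These count all reporters, before any refusal. They depend strongly on prevalence: P(at least 23) is 0.05 at 8%, 0.62 at 12% and 0.94 at 15%. Counting stools received therefore cannot by itself secure 20 in the reporter cells, and any such rule needs an end-of-round stop.

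**4. The sentences side by side.** The design sentence gives 40 per arm per round in two cells. The selection sentence takes the first 20 in each report group and asks them, so a refusal could shrink the cell. The counter runs until 20 have agreed, which implies that refusals are passed over, and it names only the arm. None of the three mentions stools received.

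**The case against.** Several stronger readings are tempting, and the protocol does not support them.

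- A reader might infer that lost stools are never replaced, or that there is one collection attempt only. The protocol does not say so. It says when the container is collected and is silent on what follows a missed collection. Only the absence of any provision can be stated.
- A reader might infer that the team stops at 20 per arm, giving 40 per round, 80 overall, and ±9.3 points with 40 per predictive value. The explicit totals of 80 and 160 rule this out. The sentence just before the counter uses the same compressed form, so the wording is most naturally shorthand for 20 per report group in each arm.
- A reader might infer that non-reporters return fewer stools because their children pass stools less often, which would bias the negative predictive value. No passage gives stool frequency or return by group. Reported diarrhoea covers the past two weeks, so a reporting child need not have loose stools on the collection day.

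It can also be said that handling a missed collection is a field detail, that the missing-data sentence would make losses visible, and that half-widths up to ±7.3 are still close to the stated ±7. The point on size stands, and it limits the weight of the concern. The rest does not remove it: reporting a loss does not make it good, and the protocol chose to state a closing rule, which counts something other than what the design requires.

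**Conclusion.** The point holds as a correctable fault in a stated field rule. The counter is tied to consents per arm, whereas the design and the ±7 points need tested stools in each of four cells per round, and nothing provides for non-return. The expected harm is modest: under 1 point of half-width at 80% return and about 1.3 points at 70%, against ±6.6 with full return. These figures rest on assumed return rates, equal return in all cells, and pooling over arms and rounds as the stated ±7 implies.

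The loss is largely avoidable for the negative predictive value, where households are plentiful. For the positive predictive value it is only partly avoidable at the protocol's 10% prevalence. The per-arm wording is loose drafting to bring into line with the totals and does not halve the sample. The budget in Appendix 2 for 120 laboratory tests against 160 planned stools is a separate inconsistency, which this point neither creates nor resolves.

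**What to change.** Replace the counter sentence in Stool sampling with:

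> Each of the four cells (arm by report status) at each time point stays open until 20 labelled, adequate stools have been received (barcode scanned at collection), or until all households in the round have been surveyed. A non-returned sample is recorded with its reason and its place is reopened. Numbers asked, consenting and returned are reported per cell.

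The scan at collection must be specified because the protocol has containers scanned but does not say when. The end-of-round clause is needed because the reporter cells may not fill. The reported counts show how far each cell fell short and whether return differed by group.

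The cost is the wording, a four-cell tally in place of a consent count, a few extra containers, and a short delay in closing a cell. Because collection lags consent by a day, a few surplus stools may arrive after a cell reaches 20; the protocol should say beforehand whether these are tested.

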Appendix 2: Budget

- Laboratory work: 129 USD per test X 120 = 15,480 USD (12,090 GBP)
- Faecal occult tests: 50 GBP for 100
- Research Assistants: 60 GBP per week X 6 weeks X 4 RAs = 1,440 GBP (salary based on interpreter salary from NGOs in Cox's Bazar)
- RA local travel: 4 RAs X 28 days X 2 GBP per day = 230
- Equipment: 100 GBP Lenovo Tab8 Tablet X5 = 500GBP
- Travel for [name]: 2870 GBP
- Two surveillance visits for icddr,b: 1094 USD = 855GBP
- Stool Sample Shipping: 12USD * 2 shipments = 24USD = 19GBP
- Icddr,b admin support fee: 1950 GBP

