
Has this child had 3 or more loose or watery stools any day in the past 2 weeks?	Yes	No
Has this child had blood in their stool in the past 2 weeks?	Yes	No

If yes to either, did you seek treatment for either of these?	Yes	No	
	lf yes, where?		

Enhanced Survey (50% of respondants)

IDENTIFY OLDEST CHILD UNDER 5												
Mid-Upper Arm Circumference			cm									
*SHOW AMSTERDAM	Consistency	А	В	С	D			_				
CHART*Has the child had any of these stools in the past 2 weeks	Colour	1	2	3	4	5	6					
How long ago?	1		2			3		4	5	6	7	Other:
How many times on the worst day?	1		2			3		4	5	6	7	Other:
How many days did it last?	1		2			3		4	5	6	7	Other:

References

- 1. Vonberg, Ralf P., et al. "Duration of Fecal Shedding of Shiga Toxin–Producing Escherichia Coli O104:H4 in Patients Infected During the 2011 Outbreak in Germany: A Multicenter Study." *Clinical Infectious Diseases*, vol. 56, no. 8, 2013, pp. 1132–1140., doi:10.1093/cid/cis1218.
- 2. ECDC. Systematic Review on the Incubation and Infectiousness/Shedding Period of Communicable Diseases in Children. 2016, Systematic Review on the Incubation and Infectiousness/Shedding Period of Communicable Diseases in Children, ecdc.europa.eu/sites/portal/files/media/en/publications/Publications/systematic-review-incubation-period-shedding-children.pdf.
- 3. Murase, T, et al. "Fecal Excretion of Salmonella Enterica Serovar Typhimurium Following a Food-Borne Outbreak." *JOURNAL OF CLINICAL MICROBIOLOGY*, vol. 38, no. 9, 2000.
- 4. Gunn, John S., et al. "Salmonella Chronic Carriage: Epidemiology, Diagnosis, and Gallbladder Persistence." *Trends in Microbiology*, vol. 22, no. 11, 2014, pp. 648–655., doi:10.1016/j.tim.2014.06.007.
- 5. Janssen, R., et al. "Host-Pathogen Interactions in Campylobacter Infections: the Host Perspective." *Clinical Microbiology Reviews*, vol. 21, no. 3, 2008, pp. 505–518., doi:10.1128/cmr.00055-07.
- 6. South Australia Health. "Shigella Infection Including Symptoms, Treatment and Prevention." SA Health, 2018, www.sahealth.sa.gov.au/wps/wcm/connect/public+content/sa+health+internet/health+topics/health+conditions+prevention+and+treatment/infe ctious+diseases/shigella+infection/shigella+infection+-+including+symptoms+treatment+and+prevention.
- 7. Weil, Ana A., et al. "Bacterial Shedding in Household Contacts of Cholera Patients in Dhaka, Bangladesh." *The American Journal of Tropical Medicine and Hygiene*, vol. 91, no. 4, 2014, pp. 738–742., doi:10.4269/ajtmh.14-0095.

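### The planned survey-versus-stool dysentery ratio cannot be read as reporting accuracy: carers report blood seen over two weeks, and no stool test in the protocol measures that

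*Protocol*

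**What the plan says.** The protocol's Data analysis section lists "Incidence rate ratios and associated 95% confidence intervals comparing diarrhoea and dysentery incidence between" two pairs of methods. The second pair is "Survey method and stool analysis method". Dysentery is therefore one of two outcomes to be contrasted between what carers say and what the stool shows. The section does not say which stool result counts as dysentery.

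On the survey side, the basic form in Appendix 3 asks: "Has this child had blood in their stool in the past 2 weeks". The sample enhanced form has no explicit blood question. It records stool consistency and colour from a chart, then timing, frequency and duration.

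On the stool side, the Stool sampling section states: "Stool will also be tested for blood using a faecal hemooccult test". Appendix 2 prices the same test ("Faecal occult tests: 50 GBP for 100") and lists no other test for blood. The remaining stool results are PCR for the listed organisms, calprotectin and lactoferrin. Inspection of the stool for visible blood is not described. On timing: "The consenting households will be given a stool collection container once the survey has been administered, which will be collected the following day".

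**The concern.** A comparison of survey and stool results informs on reporting only if both sides aim at the same condition over the same period. Here neither holds.

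- **Different construct.** The carer's answer rests on blood that was seen. An occult test is meant to find blood that may not be visible. A carer who correctly answers no can have a child who tests positive.
- **Different window.** The answer covers two weeks, while the stool result covers one sample. A carer who correctly reports an episode from ten days ago can have a child whose sample is negative.

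The study asks how accurate self-report is, so a dysentery ratio away from 1 invites the reading that carers under-report or over-report. That reading could be produced entirely by the choice of comparator.

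**Working it through.** The protocol gives no figure for this comparison, so there is nothing to reproduce. The check is what ratio to expect if every carer reports perfectly.

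**Inputs, all assumed because the protocol gives none of them:**
- v: share of children with visible blood at any time in the past two weeks.
- f: share of those children whose next-day sample is occult-positive.
- o: share occult-positive among children with no visible blood in the two weeks.

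Both sides are taken in the same children, and occult positivity is taken to stand for dysentery.

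**Formula.** With perfect carers the survey-positive share is v and the stool-positive share is v·f + (1 − v)·o, so

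ratio = v / [v·f + (1 − v)·o].

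| v | f | o | v·f | (1 − v)·o | ratio |
|---|---|---|---|---|---|
| 5% | 30% | 1% | 0.0150 | 0.0095 | 2.04 |
| 5% | 30% | 5% | 0.0150 | 0.0475 | 0.80 |
| 5% | 30% | 10% | 0.0150 | 0.0950 | 0.45 |
| 5% | 100% | 5% | 0.0500 | 0.0475 | 0.51 |
| 10% | 30% | 2% | 0.0300 | 0.0180 | 2.08 |
| 10% | 30% | 20% | 0.0300 | 0.1800 | 0.48 |

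**Direction.** The ratio is below 1 only if (1 − v)·o exceeds v·(1 − f). The break-even is o = v(1 − f)/(1 − v):
- v = 5%, f = 30%: 0.05 × 0.70 / 0.95 = 3.7%.
- v = 10%, f = 30%: 0.10 × 0.70 / 0.90 = 7.8%.

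The row with f = 100% isolates the construct mismatch: with no loss over the window, any o above zero puts the ratio below 1. Letting f fall brings in the window mismatch, which pushes the ratio up.

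**A ratio of 1 would not show agreement either.** At the first break-even, 0.05 × 0.70 = 3.5% of children are survey-positive and stool-negative, and an equal 3.5% are the reverse. Only 0.05 × 0.30 = 1.5% are positive on both.

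**Using another listed stool result.** PCR shows that an organism is present. The Executive Summary itself expects asymptomatic infection, and the organism table gives 35-69 days of carriage in children for Shiga toxin-producing E. coli, well beyond a 14-day recall window. Calprotectin and lactoferrin are described as markers of infection. None of these measures blood that a carer saw, so a perfectly reporting carer can disagree with any of them.

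**The case against.** **The protocol never says that occult positivity defines dysentery.** This is right, and the table above is conditional on that choice. PCR for Shigella, enteroinvasive E. coli or Entamoeba histolytica could be used instead, and a derived variable of this kind is often left to the statistical analysis plan, which is not shown. What does not follow is that a definition would rescue the comparison. No listed stool result measures visible blood, and no field records it on the collected sample. An analysis plan can drop the comparison, but it cannot recover an observation that was not made.

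**A reader might infer that the comparison must show under-reporting.** The documents do not support this. If the recall window is ignored and the ratio is taken simply as visible share over occult-positive share, assumed values of 1-3% and 5-20% give 0.01/0.20 = 0.05 to 0.03/0.05 = 0.60, an apparent under-reporting of 40-95%. Those ranges never let the visible share reach the occult share, so a ratio below 1 is built in. A low visible share is also doubtful, because half the stools come from households reporting diarrhoea. No such percentage should be quoted.

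**The explicit blood item is in one arm only.** This stands. By design 80 of the 160 stools come from the basic arm. The sample enhanced form records stool appearance but does not say which answers, if any, would count as dysentery.

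**Recording visible blood on the sample would not suffice.** This also stands. If f is now the share of two-week cases whose sampled stool still shows blood, the ratio under perfect reporting is 1/f, for example 1/0.30 = 3.3.

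**Importance.** The primary outcomes are the predictive values of reported diarrhoea for enteric infection. Dysentery does not enter them.

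**Conclusion.** The point holds in a limited form. The protocol names a dysentery ratio between survey and stool, but none of its stool tests measures what the basic form asks. Survey and stool results will disagree under perfect reporting, so the ratio is not a measure of reporting accuracy.

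Its size and sign cannot be given from the documents. Under the assumed values tabulated, perfect carers yield ratios from 0.45 to 2.08. Occult-only blood lowers the ratio, and the two-week window raises it. The structural conclusion needs only two things: some children can be occult-positive without visible blood, and some reported episodes can have ended before the sample.

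This is a secondary analysis and the primary predictive values are untouched. It is still worth changing, because the comparison is written into the protocol and would be read as bearing on the study's main question.

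**What to change.** In the Data analysis section:
1. Remove dysentery from the survey-versus-stool rate ratio.
2. State that occult positivity is not the stool-side measure of dysentery.
3. Report occult positivity separately as a marker, by report group (blood reported yes or no, in the basic arm).

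Optionally, add one yes/no field for visible blood on each collected stool and present it descriptively. State with it that it covers one stool while the survey covers two weeks. It would bear on reporting accuracy only if the carer were also asked about the same day.

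**Cost.** The text change is a few sentences, and one secondary comparison is lost. The optional item is one tick box on up to 160 stools. Visible blood is likely to be too rare among them for a precise estimate.
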